**2. LIST OF ABBREVIATIONS**

Term	Definition / description
AE	Adverse Event
BRPM	Blinded Report Planning Meeting
BES	Biopsy Evaluable Set
CTC	Common Terminology Criteria
CTP	Clinical Trial Protocol
CTR	Clinical Trial Report
DM&SM	Boehringer Ingelheim Data Management And Statistics Manual
DRA	Drug Regulatory Affairs
DM	Diabetes mellitus
DMG	Dictionary Maintenance Group
EDC	Electronic Data Capture
EMEA	European Agency For The Evaluation Of Medicinal Products
FAS	Full Analysis Set
HPT	Hypertension
ICH	International Conference On Harmonisation
IPD	Important Protocol Deviation
LOCF	Last Observation Carried Forward
MedDRA	Medical Dictionary For Regulatory Activities
MCPMod	Multiple Comparison Procedure and Modelling
MQRM	Medical Quality Review Meeting
MMRM	Mixed Effect Model Repeated Measurement
PASI	Psoriasis Area Severity Index
PCR	Pol y m erase Chain Reaction
PK	Pharmacokinetics
PKS	Pharmacokinetics Set
PPS	Per Protocol Set
PSTAT	Project Statistician
PT	Preferred Term
PV	Protocol Violation
QI	Lower Quartile

Term	Definition / description
Q3	Upper Quartile
REP	Residual Effect Period
RS	Randomised Set
SA	Statistical Analysis
SD	Standard Deviation
SMQ	Standardised MedDRA Query
SOC	System Organ Class
sPGA	Static Physician's Global Assessment
TOM	Trial Oversight Meeting
ToC	Table of Contents
TS	Treated Set
TSAP	Trial Statistical Analysis Plan

### **3. INTRODUCTION**

As per ICH E9 ill, the purpose of this document is to provide a more technical and detailed elaboration of the principal features of the analysis described in the protocol, and to include detailed procedures for executing the statistical analysis of the primary and secondary variables and other data.

This TSAP assumes familiarity with the Clinical Trial Protocol (CTP), including Protocol Amendments. In particular, the TSAP is based on the planned analysis specification as written in CTP Section 7 "Statistical Methods and Determination of Sample Size". Therefore, TSAP readers may consult the CTP for more background information on the study, e.g., on study objectives, study design and population, treatments, definition of measurements and variables, planning of sample size, randomization.

The trial data is stored in the BI Rave (BRAVE) database system.

S A S® Version 9.4 will be used for analyses.

**4. CHANGES IN THE PLANNED ANALYSIS OF THE STUDY**

This section is not applicable as no change has been made.

**5. ENDPOINTS**

**5.1 PRIMARY ENDPOINTS**

Please refer to protocol.

[figure not shown]
**5.2 SECONDARY ENDPOINTS**

**5.2.1 Key secondary endpoints**

This section is not applicable as no key secondary endpoint has been specified in the protocol

**5.2.2 Secondary endpoints**

Please refer to CTP.

## **6. GENERAL ANALYSIS DEFINITIONS**

### **6.1 TREATMENTS**

Patients will be randomised 1:1 to BI 764198 treatment group or placebo.

The assignment of treatment groups will be based on randomization for randomized patient set as defined in Section 6.3.

The following study periods based on actual start and stop dates of study treatment administration are defined:

**Table 6.1: 1 Definition of treatment periods**

Analysing Treatment Period	Start Date (including)	Stop Date (including)
Screening	Day of informed consent	Date of first administration of study medication -1 day (It could be the same day of informed consent)
On-treatment period	Day of first administration of study medication	
Post-treatment		Last contact date

For detailed rules for assigning AEs to these time periods, please refer to Section 7.8.1.

### **6.2 IMPORTANT PROTOCOL DEVIATION**

A protocol deviation (PD) is important if it affects the rights or safety of the study subjects, or if it can potentially influence the primary outcome measurement(s) in a non-negligible way. Patients with important PDs that could potentially impact the evaluation of the primary endpoint(s) will be excluded from PPS, if applicable.

Handling of iPDs in analysis is included in the DV domain specifications and stored within the TMF in EDMS. Important PDs will be reviewed at Medical Quality Review Meetings (MQRMs) conducted periodically during the trial. A list of protocol deviations will be discussed at the Blinded Report Planning Meetings (BRPMs).

If the data show other important PDs, this table will be supplemented accordingly at BRPMs or through team review of the manual PD log. The decision whether a subject will

Proprietary confidential information © 2021 Boehringer Ingelheim International GmbH or one or more of its affiliated companies

be excluded from the analysis will be made at the final BRPM prior to Database Lock (DBL).

Handling of IPDs in analysis is included in the DV domain specifications and stored within the TMF in EDMS.

### **6.3 SUBJECT SETS ANALYSED**

There are 4 patient sets defined in this trial:

- Screened Set (SCR)

This set includes all patients with signed informed consent. The screened set will be used for disposition summaries.

- Randomised Set (RS)

The RS includes all patients who signed the informed consent form and were also randomised, regardless whether the patient was treated with trial medication or not. The randomized set will be used for analysis of important protocol deviations (IPDs).

- Full Analysis Set (FAS)

The FAS includes all patients in the RS who received at least 1 dose of trial medication. The FAS is used for efficacy and safety analyses.

- Per Protocol Set (PPS)

The PPS includes all patients from the FAS without IPDs leading to exclusion from per protocol analysis. The PPS is used for efficacy sensitivity analyses only if the number of patients with IPDs is > 10% of total number of patients in FAS.

Analyses will be performed as outlined in Table 6.3: 1.

**Table 6.3: 1 Patient sets analysed**

[figure not shown]
Class of endpoint	Patient set			
	Screened set	Full analysis set	Randomised set	Per Protocol Set
Efficacy analysis		X	si	02
Safety analysis		X		
Patients disposition	X			

 S = Sensitivity analyses

 0 : Optional

The FAS will be used for the efficacy analyses following the intention-to-treat (ITT) principle in assigning patients to treatment groups, i.e., efficacy analyses will be analysed as randomised using the FAS.

If a patient receives incorrect medication for the entire treatment period, efficacy will be analysed as randomized and safety will be analysed as treated. If a patient receives incorrect medication for part of the treatment period, such cases will be discussed in the RPM.

## **6.5 POOLING OF CENTRES**

This section is not applicable because centre/country is not included in the statistical model.

## **6.6 HANDLING OF MISSING DATA AND OUTLIERS**

All patients will be followed to collect necessary efficacy and safety information, even if patients discontinue study medication prematurely.

For patients who miss WHO clinical progression scales, imputation will be performed using data from other sources if available, e.g., oxygen use, ventilation use, etc.

For patients who miss start date and/or end date of hospitalisation, ventilator use and oxygen use, data will be imputed based on available information on the eCRF page of WHO Clinical Progression Scales.

Proprietary confidential information © 2021 Boehringer Ingelheim International GmbH or one or more of its affiliated companies

If a patient dies while hospitalised, the number of days of hospitalisation will be imputed until day 29 (i.e. 28 days of hospitalisation). If a patient dies while in ICU, the duration of ICU stay will be imputed until day 29. For patients who die before day 29, WHO progression scale will be imputed as 10 for all remaining visits: in addition, duration of oxygen (or ventilation) use will be imputed until day 29.

For patients who are discharged before day 29, WHO progression scale will be imputed using the last available observation if no additional data is available after discharge.

For patients who discontinue treatment early, if the patient is on oxygen/ventilation before discontinuation, the number of days on oxygen/ventilation will be imputed until day 29. If the patient is not on mechanical ventilator at the last observed assessment, the number of ventilator free days will be imputed until day 29.

For missing or incomplete AE dates, BI internal procedures and guidelines will be followed Q2J1. The same philosophy will be applied to missing concomitant medication dates (where applicable), and dates of study medication discontinuation, and trial completion date.

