5.1.3 Other efficacy assessments

The duration of, and time to, ICU admission, the number of ventilator-free and oxygen-free days, the initiation of new ventilation use, and duration of hospitalisation will be derived from source documents. The date of discharge from hospital and/or death will be recorded on the eCRF.

The Clinical Frailty Scale (CFS) [[R20-2080](#)] will be determined at the time point indicated on the [Flow Chart](#). The CFS is a means of summarising the overall level of fitness or frailty of an individual. It comprises a 9-point scale with categories ranging from 1 (very fit) to 9 (terminally ill).

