7.3 HANDLING OF MISSING DATA

All attempt will be made to collect all data per protocol.

For patients who miss Clinical Progression Scales, imputation will be performed using data from other sources if available, e.g., oxygen use, ventilation use, etc.

For patients who miss start date and/or end data of hospitalisation, ventilator use and oxygen use, data will be imputed based on available Clinical Progression Scales. If a patient dies while hospitalised, the number of days of hospitalisation will be imputed as 28 days.

Further details will be specified in the TSAP.

[figure not shown]

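### SAP 6.6 penalises death in ICU duration only when it occurs in ICU, so a death elsewhere before Day 29 can score 0 ICU days; hospital duration has a smaller gap, for deaths after discharge

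*SAP*

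**What the plan says.** SAP 6.6 has separate rules for what happens to each duration when a patient dies.

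- **ICU stay:** "If a patient dies while in ICU, the duration of ICU stay will be imputed until day 29". The condition is death in ICU.
- **Hospital stay:** Protocol 7.3 states: "If a patient dies while hospitalised, the number of days of hospitalisation will be imputed as 28 days". SAP 6.6 keeps the same in-hospital condition and the same 28 days. Protocol 7.3 has no ICU rule.
- **WHO scale:** "For patients who die before day 29, WHO progression scale will be imputed as 10 for all remaining visits". There is no condition on place of death.
- **Oxygen and ventilation:** the same sentence continues "in addition, duration of oxygen (or ventilation) use will be imputed until day 29", again for deaths before Day 29 in any place.

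Protocol 5.1.3 lists the measures to be derived from source documents: "The duration of, and time to, ICU admission, the number of ventilator-free and oxygen-free days, the initiation of new ventilation use, and duration of hospitalisation". ICU duration and hospital duration are therefore derived efficacy measures, but neither is in the list of primary and secondary endpoints in Protocol 2.1.

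**The concern.** Extending ICU stay to Day 29 for deaths in ICU shows that the SAP does not want an early death to look like a short, favourable stay. The rule achieves this only for one place of death. A patient who dies on the ward without entering ICU has 0 ICU days, the same as a patient who never deteriorated and fewer than a survivor with a short ICU stay. A patient who leaves ICU and later dies on the ward keeps only the days spent there. Two equally bad outcomes thus receive very different scores.

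ICU duration could then move in the wrong direction: a treatment that turned ward deaths into survivals with an ICU stay would appear to lengthen ICU use. For hospital duration the same can happen only with a death after discharge, where the patient keeps the short stay up to discharge.

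**Working it through.** **1. The plan's own figure.** From Day 1 to Day 29: 29 − 1 = 28 days. This reproduces the 28 hospital days in SAP 6.6 and Protocol 7.3.

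**2. SAP 6.6 applied to example patients.** The patients are invented. ICU days are end day minus admission day, or 29 minus admission day for a death in ICU.

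| Patient | ICU days under SAP 6.6 |
|---|---|
| Survivor, never in ICU | 0 |
| Ward death on Day 10, never in ICU | 0 |
| Ward death on Day 15, in ICU Days 3 to 6 | 6 − 3 = 3 |
| Survivor, in ICU Days 5 to 10 | 10 − 5 = 5 |
| ICU death on Day 10, admitted Day 5 | 29 − 5 = 24 |

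The first ward death ties with the best survivor. Both ward deaths score better than the survivor who needed ICU. All three patients who died receive 28 hospital days, so the hospital rule works for them.

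**3. Effect on an arm mean.** Inputs: 65 patients per arm (Protocol synopsis); k deaths outside ICU with no ICU stay (assumed); analysis over all patients (assumed). Scoring each such death 0 instead of 28 lowers the mean by k × 28 / 65:

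- k = 2: 56 / 65 = 0.86 days
- k = 3: 84 / 65 = 1.29 days
- k = 4: 112 / 65 = 1.72 days

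**4. Direction of a treatment difference.** Suppose, purely as an illustration, that 3 ward deaths on placebo become 3 survivors with 6 ICU days each on drug, and nothing else differs.

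- SAP rule, drug minus placebo: (3 × 6 − 3 × 0) / 65 = +0.28 days, so drug looks worse.
- All deaths at 28 days: (3 × 6 − 3 × 28) / 65 = −1.02 days, so drug looks better.

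The sign changes for any death value above 6 days.

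**5. Place of death alone.** Assume 10 deaths among 65 patients, no ICU days in survivors, ICU deaths admitted on Day 5 (24 days each), and ward deaths never in ICU.

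- All 10 in ICU: 240 / 65 = 3.69 days
- 5 in ICU and 5 on the ward: 120 / 65 = 1.85 days
- All 10 on the ward: 0 days

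Mortality is identical in all three cases. With 28 days for every death the mean is 280 / 65 = 4.31 in each.

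**The case against.** The strongest reply is that no visible analysis uses these numbers. SAP 7.5.2 does not analyse ICU or hospital duration. Any text that does, such as SAP 7.6 or Section 10, is not in the available version, so a summary limited to admitted patients, or a further rule for deaths, cannot be ruled out. In a summary of admitted patients only, the never-admitted death would be left out rather than scored as best. This stands, and it is why the size above is conditional on an all-patient analysis.

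Death is also counted where the trial draws its conclusions. A reader might infer that ward deaths escape the efficacy results; the documents do not support that. A death by Day 29 fails the primary endpoint, enters the mortality endpoints, counts in the secondary composite if it occurs in hospital, and scores WHO 10 from then on. Protocol 7.1 plans no formal testing. A reader might also infer that hospital duration has the same defect as ICU duration. It does not, because a ward death receives 28 hospital days.

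The number of non-ICU deaths is unknown. Exclusion criterion 9 removes patients not committed to full support or intubation, which makes deaths without ICU care less frequent. It does not exclude them: entry needs only WHO grade 5 or 6, not ICU care.

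The contrast with oxygen and ventilation should not be overstated. That sentence may mean only that existing use is extended. The WHO rule is clear for every death, however, and SAP 7.5.2 counts ventilator-free days from WHO scores below 7, so no day scored 10 after a death counts as ventilator free, wherever the death occurred.

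Finally, 0 ICU days is a true record of ICU use for someone never admitted. That would be a full answer if the SAP measured resource use alone. Once it extends ICU stay after a death in ICU, the measure is no longer that.

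**Conclusion.** The point holds for ICU duration as SAP 6.6 is written: a death before Day 29 outside ICU carries 0 or only the accrued ICU days, and place of death changes the score of an equally bad outcome. For hospital duration it holds only for deaths after discharge and before Day 29; no size is given for that part.

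The consequence is limited to supportive measures. The range of 0.86 to 1.72 mean ICU days rests on an assumed 2 to 4 non-ICU deaths per 65 patients with no ICU stay, an all-patient mean, and 28 days as the comparison value. The sign reversal shows what the rule permits; it is not a forecast. The documents give no standard deviation against which to judge either figure. Nothing here affects the primary or secondary endpoints.

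**What to change.** In SAP 6.6, before treatment information is released, assign every death before Day 29 the same fixed value of 28 days for both ICU and hospital duration, wherever the death occurs and including deaths in ICU. Equivalently, analyse days alive and out of ICU, or out of hospital, to Day 29 with all deaths scored 0; this is 28 minus the penalised duration.

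The value must be fixed and must apply to all deaths. Extending ICU stay to Day 29 does not work for a patient never admitted, because there is no start date. A flat 28 for non-ICU deaths alone would score them worse than the ICU death admitted on Day 5, at 24 days.

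The cost is a short rewording and no new data, since date of death and vital status are already collected. Means rise in an arm with more deaths outside ICU or after discharge, and slightly for ICU deaths: from 24 to 28 days adds 4 / 65 = 0.06 to the arm mean per such death. The measure becomes a death-penalised composite rather than pure resource use, so observed ICU days should also be reported descriptively.

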^e Interactive Response Technology (IRT) will be used to allocate a 10 day supply of study drug at Visit 2 (or at the conclusion of Visit 1 after all eligibility criteria are confirmed to be met to allow time to prepare the study drug prior to day of randomization (first administration of study drug) and, if applicable per an individual patient's treatment duration, at Visit 12 and Visit 22.

^f If the patient discontinues treatment and is not discharged prior to Day 29, collect ventilation and oxygen parameters daily up to Day 29, respiratory rate, FiO₂, SpO₂, if applicable, at Day 29, and WHO Clinical Progression Scale score at Day 29. If patient is on oxygen therapy at discharge, collect end date of that oxygen therapy when available during the Follow-up visit telephone call(s).

^g ECG should be performed 0.5-4 hours after drug administration.

^h SARS-CoV-2 PCR test to be performed as visit procedure and an approved SARS-CoV-2 point-of-care test may be used to evaluate inclusion criterion 2, refer to [Section 3.3.2](#).

ⁱ Dosing should be stopped the day prior to EOT. However, if it is uncertain whether a patient is fit for discharge, and the patient has not yet completed the allowed treatment duration of 28 days, administer study drug and perform all study procedures per the planned treatment period visit. If later that day the PI makes the decision that patient will discharge, perform any additional EOT visit procedures, if applicable, per [Flow Chart](#) and record visit in the eCRF as EOT visit.

TABLE OF CONTENTS

| | |
|---|-----------|
| TITLE PAGE | 1 |
| CLINICAL TRIAL PROTOCOL SYNOPSIS | 2 |
| FLOW CHART | 4 |
| TABLE OF CONTENTS | 6 |
| ABBREVIATIONS | 9 |
| 1. INTRODUCTION..... | 12 |
| 1.1 MEDICAL BACKGROUND | 12 |
| 1.2 DRUG PROFILE | 13 |
| 1.3 RATIONALE FOR PERFORMING THE TRIAL | 15 |
| 1.4 BENEFIT - RISK ASSESSMENT..... | 16 |
| 1.4.1 Benefits | 16 |
| 1.4.2 Risks | 16 |
| 1.4.3 Discussion..... | 17 |
| 2. TRIAL OBJECTIVES AND ENDPOINTS..... | 18 |
| 2.1 MAIN OBJECTIVES, PRIMARY AND SECONDARY ENDPOINTS..... | 18 |
| 2.1.1 Main objectives..... | 18 |
| 2.1.2 Primary endpoint(s)..... | 18 |
| 2.1.3 Secondary endpoints | 18 |
| [REDACTED] | |
| 3. DESCRIPTION OF DESIGN AND TRIAL POPULATION..... | 20 |
| 3.1 OVERALL TRIAL DESIGN..... | 20 |
| 3.2 DISCUSSION OF TRIAL DESIGN, INCLUDING THE CHOICE OF CONTROL GROUP(S)..... | 20 |
| 3.3 SELECTION OF TRIAL POPULATION | 21 |
| 3.3.1 Main diagnosis for trial entry | 22 |

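### SAP 6.6 extends oxygen and ventilation days to Day 29 after early drug stop without requiring missing data, and credits ventilator-free days with no exception for death

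*SAP*

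**What the plan says.** SAP 6.6 (Handling of missing data and outliers) opens by saying that patients are followed for efficacy and safety after stopping medication. The rules that matter here are:

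- **Missing scores and dates.** Missing WHO scores are filled from other sources such as oxygen or ventilation use. Missing hospitalisation, ventilation and oxygen dates are filled from the WHO scale page. Both rules are limited to patients whose item is missing.
- **Death.** "For patients who die before day 29, WHO progression scale will be imputed as 10 for all remaining visits". Oxygen or ventilation duration is also extended to Day 29.
- **Discharge before Day 29.** "WHO progression scale will be imputed using the last available observation if no additional data is available after discharge".
- **Early treatment discontinuation, on support.** "if the patient is on oxygen/ventilation before discontinuation, the number of days on oxygen/ventilation will be imputed until day 29".
- **Early treatment discontinuation, not ventilated.** "If the patient is not on mechanical ventilator at the last observed assessment, the number of ventilator free days will be imputed until day 29".

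SAP 7.5.2 analyses the secondary endpoints under a treatment policy estimand. It counts a day as ventilator free when the WHO score is below 7, from randomisation to Day 29.

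On data collection, protocol Flow Chart footnote f says: "If the patient discontinues treatment and is not discharged prior to Day 29, collect ventilation and oxygen parameters daily up to Day 29". For patients discharged on oxygen it adds: "If patient is on oxygen therapy at discharge, collect end date of that oxygen therapy when available", to be obtained at the follow-up calls. Protocol 5.1.3 says that "the number of ventilator-free and oxygen-free days, the initiation of new ventilation use, and duration of hospitalisation will be derived from source documents".

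**The concern.** There are two separate problems of wording.

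(a) The duration rule is triggered by stopping drug while on support, not by a gap in the data. The discharge rule just before it does carry a missing-data condition, and so do the score and date rules. Applied as written, the duration rule would replace observed oxygen and ventilation days with imputed ones in patients whom the protocol takes care to keep observing. That does not fit a treatment policy estimand, under which outcomes after drug stop are used as they occurred.

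(b) The ventilator-free-day credit has no exception for death. An early discontinuer who was unventilated when last assessed and then dies before Day 29 falls under two rules with opposite results: WHO=10, which earns no ventilator-free days from death onward, and the credit, which earns all of them.

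Two careful programmers could therefore derive different values for the same patient. Part (b) affects ventilator-free days, a named secondary endpoint analysed by ANCOVA. Part (a) affects oxygen and ventilation durations and the oxygen-free days named in protocol 5.1.3. If the choice were made after unblinding, it would be post hoc.

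**Working it through.** The plan states no figure that depends on these rules, so there is nothing to reproduce. The check applies the sentences literally to example patients, whose histories are assumed.

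**Inputs**

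- Counting window: Day 1 to Day 29 inclusive, 29 days (SAP 7.5.2).
- Ventilator free: WHO score below 7 (SAP 7.5.2).
- After death: WHO = 10 (SAP 6.6).
- Patients per arm: 65 (protocol synopsis).
- Patients are on oxygen at entry, because inclusion criterion 3 requires a WHO score of 5 or 6.

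**(a) Duration rule**

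*Oxygen.* A patient stops drug on Day 5 while on oxygen, stays in hospital to Day 29, and is seen to be off oxygen from Day 9.

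- Observed oxygen days: Days 1 to 8 = 8.
- Literal rule: Days 1 to 29 = 29.
- Difference: 29 - 8 = 21 days.
- If oxygen-free days are the complement within the window (an assumption, since the visible text does not define them), the values are 29 - 8 = 21 observed and 29 - 29 = 0 imputed.

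Footnote f would have recorded those days, so nothing needed imputing.

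*Ventilation.* A patient is ventilated on Days 4 to 10, stops drug on Day 6, is extubated on Day 11 and survives.

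- Observed ventilation days: 10 - 4 + 1 = 7.
- Literal rule: Days 4 to 29 = 29 - 4 + 1 = 26.
- Ventilator-free days by the WHO <7 count: 29 - 7 = 22.
- Sum of imputed ventilation days and ventilator-free days: 26 + 22 = 48, in a window of 29.

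The two quantities cannot both describe this patient. Ventilator-free days would change only if the imputed duration were carried into that count (29 - 26 = 3), and the SAP does not say that it is.

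**(b) Ventilator-free-day credit against the death rule**

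Take a never-ventilated early discontinuer who dies on Day *D*.

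- WHO=10 rule: ventilator-free days = *D* - 1.
- Credit rule: 29.
- Difference: 29 - (*D* - 1) = 30 - *D*.
- Shift in the unadjusted arm mean per such patient: (30 - *D*)/65.

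| Death on Day | WHO=10 rule | Credit rule | Difference | Arm-mean shift per patient |
|---|---|---|---|---|
| 5 | 4 | 29 | 25 | 25/65 = 0.38 |
| 10 | 9 | 29 | 20 | 20/65 = 0.31 |
| 15 | 14 | 29 | 15 | 15/65 = 0.23 |
| 20 | 19 | 29 | 10 | 10/65 = 0.15 |
| 28 | 27 | 29 | 2 | 2/65 = 0.03 |

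With several patients dying on the same day, the shift is this figure times their number. The documents give no discontinuation or death rates, so that number cannot be estimated.

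**The case against.** The strongest reply is that nobody would program it this way. The section is about missing data and speaks of imputation. The ventilator-free sentence refers to the last observed assessment, which presupposes that nothing was observed afterwards. SAP 7.4.1 explains treatment policy, for the primary analysis, as including data collected after drug stop, and protocol 5.1.3 derives these day counts from source documents. On death, the WHO=10 rule covers everyone who dies before Day 29, on or off drug. The WHO <7 definition then gives no credit for those days, and the companion clause extending support duration after death is also unfavourable. A score of 29 requires setting all of that aside.

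Much of this stands. A reader might infer that the SAP deliberately discards observed data or departs from its estimand. The documents do not support that; the heading and surrounding rules suggest that only missing data were meant. A reader might also infer that full credit after death is the intended scoring, but the 7.5.2 definition leans the other way.

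What does not stand is that the wording is therefore sufficient. The neighbouring rules state their missing-data condition and this one does not. The credit is a specific sentence about early discontinuers that competes with a general rule about deaths, and the supplied text does not say which prevails.

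The reply is also right that the affected group in (b) may be small. A patient must stop drug early, be unventilated at the last observed assessment and die before Day 29, and exclusion criterion 9 bars patients not committed to intubation.

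**Conclusion.** The point holds as a defect of wording with numerical consequences. Followed literally, SAP 6.6 replaces oxygen and ventilation days that the protocol collects, and gives two values for ventilator-free days in an early discontinuer who dies unventilated: 9 or 29 for a death on Day 10, or 0.31 days on a 65-patient arm mean per such patient. This rests on the 29-day inclusive count and on assumed patient histories.

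Severity is minor to moderate. The trial is exploratory with no formal testing (protocol 7.1). The primary endpoint is status at Day 29 and is not built from these day counts. No visible secondary endpoint is an oxygen or ventilation duration, so (a) bears on those durations and on the oxygen-free days of protocol 5.1.3, while (b) bears on a secondary endpoint.

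Three further inferences are not supported:

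- **That the treatment comparison is biased.** Without discontinuation or death rates by arm, bias is possible but not shown.
- **That the full SAP has no precedence rule.** Some SAP passages are not in the supplied text and could contain one.
- **That the planned sensitivity analysis excluding deaths in the treatment period is defective or undefined.** Protocol 6.2.2 runs that period from Visit 2 to the EOT visit, the stop date in the SAP's period table is not readable in the supplied text, and the main analysis keeps the deaths.

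**What to change.** Before unblinding, add two statements to SAP 6.6:

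1. The early-discontinuation rules apply only to days with no observed data, after the section's existing rules for filling gaps from other sources have been used.
2. The death rule overrides the ventilator-free-day credit: WHO = 10 from death, so no ventilator-free days from that day onward.

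If a passage not supplied here already says this, a cross-reference in 6.6 is enough.

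The cost is SAP text and a small change to derivation code, with no new data collection. Some imputation will remain. After drug stop, footnote f asks for the WHO score only at Day 29, so daily scores have to be rebuilt from the ventilation and oxygen records. After discharge, the oxygen end date is collected only when available.
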